14.2 Protocol Deviations

The investigator should not deviate from the protocol, except where necessary to eliminate an immediate hazard to study subjects. Should other unexpected circumstances arise that will require deviation from protocol-specified procedures, the investigator should consult with the sponsor or designee (and IRB or IEC, as required) to determine the appropriate course of action. There will be no exemptions (a prospectively approved deviation) from the inclusion or exclusion criteria.

The site should document all protocol deviations in the subject's source documents. In the event of a significant deviation, the site should notify the sponsor or its designee (and IRB or EC, as required). Significant deviations include, but are not limited to, those that involve fraud or misconduct, increase the health risk to the subject, or confound interpretation of primary study assessment. A Protocol Deviation Form should be completed by the site and signed by the sponsor or designee for any significant deviation from the protocol.

14.3 Quality Assurance Audits and Regulatory Agency Inspections

The study site also may be subject to quality assurance audits by the sponsor or designees. In this circumstance, the sponsor-designated auditor will contact the site in advance to arrange an auditing visit. The auditor may ask to visit the facilities where laboratory samples are collected, where the medication is stored and prepared, and any other facility used during the study. In addition, there is the possibility that this study may be inspected by regulatory agencies, including those of foreign governments (eg, the Food and Drug Administration [FDA], the United Kingdom Medicines and Healthcare products Regulatory Agency, the Pharmaceuticals and Medical Devices Agency of Japan). If the study site is contacted for an inspection by a regulatory body, the sponsor should be notified immediately. The investigator and institution guarantee access for quality assurance auditors to all study documents as described in Section 14.1.

CONFIDENTIAL

15.0 ETHICAL ASPECTS OF THE STUDY

This study will be conducted with the highest respect for the individual participants (ie, subjects) according to the protocol, the ethical principles that have their origin in the Declaration of Helsinki, and the ICH Harmonised Tripartite Guideline for GCP. Each investigator will conduct the study according to applicable local or regional regulatory requirements and align his or her conduct in accordance with the “Responsibilities of the Investigator” that are listed in Appendix B. The principles of Helsinki are addressed through the protocol and through appendices containing requirements for informed consent and investigator responsibilities.

15.1 IRB and/or IEC Approval

IRBs and IECs must be constituted according to the applicable local requirements of each participating region. The sponsor or designee will require documentation noting all names and titles of members who make up the respective IRB or IEC. If any member of the IRB or IEC has direct participation in this study, written notification regarding his or her abstinence from voting must also be obtained. Those Americas sites unwilling to provide names and titles of all members due to privacy and conflict of interest concerns should instead provide a Federal Wide Assurance Number or comparable number assigned by the Department of Health and Human Services.

The sponsor or designee will supply relevant documents for submission to the respective IRB or IEC for the protocol's review and approval. This protocol, the Investigator's Brochure, a copy of the informed consent form, and, if applicable, subject recruitment materials and/or advertisements and other documents required by all applicable laws and regulations, must be submitted to a central or local IRB or IEC for approval. The IRB's or IEC's written approval of the protocol and subject informed consent must be obtained and submitted to the sponsor or designee before commencement of the study (ie, before shipment of the sponsor-supplied drug or study specific screening activity). The IRB or IEC approval must refer to the study by exact protocol title, number, and version date; identify versions of other documents (eg, informed consent form) reviewed; and state the approval date. The sponsor will notify site once the sponsor has confirmed the adequacy of site regulatory documentation and, when applicable, the sponsor has received permission from competent authority to begin the trial. Until the site receives notification no protocol activities, including screening may occur.

Sites must adhere to all requirements stipulated by their respective IRB or IEC. This may include notification to the IRB or IEC regarding protocol amendments, updates to the informed consent form, recruitment materials intended for viewing by subjects, local safety reporting requirements, reports and updates regarding the ongoing review of the study at intervals specified by the respective IRB or IEC, and submission of the investigator's final status report to IRB or IEC. All IRB and IEC approvals and relevant documentation for these items must be provided to the sponsor or its designee.

Subject incentives should not exert undue influence for participation. Payments to subjects must be approved by the IRB or IEC and sponsor.

15.2 Subject Information, Informed Consent, and Subject Authorization

Written consent documents will embody the elements of informed consent as described in the Declaration of Helsinki and the ICH Guidelines for GCP and will be in accordance with all applicable laws and regulations. The informed consent form, subject authorization form (if applicable), and subject information sheet (if applicable) describe the planned and permitted uses, transfers, and disclosures of the subject's personal and personal health information for purposes of conducting the study. The informed consent form and the subject information sheet (if applicable) further explain the nature of the study, its objectives, and potential risks and benefits, as well as the date informed consent is given. The informed consent form will detail the requirements of the participant and the fact that he or she is free to withdraw at any time without giving a reason and without prejudice to his or her further medical care.

The investigator is responsible for the preparation, content, and IRB or IEC approval of the informed consent form and if applicable, the subject authorization form. The informed consent form, subject authorization form (if applicable), and subject information sheet (if applicable) must be approved by both the IRB or IEC and the sponsor prior to use.

The informed consent form, subject authorization form (if applicable), and subject information sheet (if applicable) must be written in a language fully comprehensible to the prospective subject. It is the responsibility of the investigator to explain the detailed elements of the informed consent form, subject authorization form (if applicable), and subject information sheet (if applicable) to the subject. Information should be given in both oral and written form whenever possible and in the manner deemed appropriate by the IRB or IEC. In the event the subject is not capable of rendering adequate written informed consent, then the subject's legally acceptable representative may provide such consent for the subject in accordance with applicable laws and regulations.

The subject, or the subject's legally acceptable representative, must be given ample opportunity to: (1) inquire about details of the study and (2) decide whether or not to participate in the study. If the subject, or the subject's legally acceptable representative, determines he or she will participate in the study, then the informed consent form and subject authorization form (if applicable) must be signed and dated by the subject, or the subject's legally acceptable representative, at the time of consent and prior to the subject entering into the study. The subject or the subject's legally acceptable representative should be instructed to sign using their legal names, not nicknames, using blue or black ballpoint ink. The investigator must also sign and date the informed consent form and subject authorization (if applicable) at the time of consent and prior to subject entering into the study; however, the sponsor may allow a designee of the investigator to sign to the extent permitted by applicable law.

Once signed, the original informed consent form, subject authorization form (if applicable), and subject information sheet (if applicable) will be stored in the investigator's site file. The investigator must document the date the subject signs the informed consent in the subject's medical record. Copies of the signed informed consent form, the signed subject authorization form (if applicable), and subject information sheet (if applicable) shall be given to the subject.

All revised informed consent forms must be reviewed and signed by relevant subjects or the relevant subject's legally acceptable representative in the same manner as the original informed consent. The date the revised consent was obtained should be recorded in the subject's medical record, and the subject should receive a copy of the revised informed consent form.

15.3 Subject Confidentiality

The sponsor and designees affirm and uphold the principle of the subject's right to protection against invasion of privacy. Throughout this study, a subject's source data will only be linked to the sponsor's clinical study database or documentation via a unique identification number. As permitted by all applicable laws and regulations, limited subject attributes, such as sex, age, or date of birth, and subject initials may be used to verify the subject and accuracy of the subject's unique identification number.

To comply with China GCP, ICH Guidelines for GCP and to verify compliance with this protocol, the sponsor requires the investigator to permit its monitor or designee's monitor, representatives from any regulatory authority (eg, CFDA, FDA, Medicines and Healthcare products Regulatory Agency, Pharmaceuticals and Medical Devices Agency), the sponsor's designated auditors, and the appropriate IRBs and IECs to review the subject's original medical records (source data or documents), including, but not limited to, laboratory test result reports, ECG reports, admission and discharge summaries for hospital admissions occurring during a subject's study participation, and autopsy reports. Access to a subject's original medical records requires the specific authorization of the subject as part of the informed consent process (see Section 15.2).

Copies of any subject source documents that are provided to the sponsor must have certain personally identifiable information removed (ie, subject name, address, and other identifier fields not collected on the subject's eCRF).

15.4 Publication, Disclosure, and Clinical Trial Registration Policy

15.4.1 Publication and Disclosure

The investigator is obliged to provide the sponsor with complete test results and all data derived by the investigator from the study. During and after the study, only the sponsor may make study information available to other study investigators or to regulatory agencies, except as required by law or regulation. Except as otherwise allowable in the clinical study site agreement, any public disclosure (including publicly accessible websites) related to the protocol or study results, other than study recruitment materials and/or advertisements, is the sole responsibility of the sponsor.

The sponsor may publish any data and information from the study (including data and information generated by the investigator) without the consent of the investigator. Manuscript authorship for any peer-reviewed publication will appropriately reflect contributions to the production and review of the document. All publications and presentations must be prepared in accordance with this section and the Clinical Study Site Agreement. In the event of any discrepancy between the protocol and the Clinical Study Site Agreement, the Clinical Study Site Agreement will prevail.

CONFIDENTIAL

15.4.2 Clinical Trial Registration

In order to ensure that information on clinical trials reaches the public in a timely manner and to comply with applicable laws, regulations and guidance, Takeda will, at a minimum register interventional clinical trials it sponsors anywhere in the world on ClinicalTrials.gov or other publicly accessible websites before start of study, as defined in Takeda Policy/Standard. Takeda contact information, along with investigator's city, state (for Americas investigators), country, and recruiting status will be registered and available for public viewing.

For some registries, Takeda will assist callers in locating trial sites closest to their homes by providing the investigator name, address, and phone number to the callers requesting trial information. Once subjects receive investigator contact information, they may call the site requesting enrollment into the trial. The investigative sites are encouraged to handle the trial inquiries according to their established subject screening process. If the caller asks additional questions beyond the topic of trial enrollment, they should be referred to the sponsor.

Any investigator who objects to Takeda providing this information to callers must provide Takeda with a written notice requesting that their information not be listed on the registry site.

15.4.3 Clinical Trial Results Disclosure

Takeda will post the results of clinical trials on ClinicalTrials.gov or other publicly accessible websites, as required by Takeda Policy/Standard, applicable laws and/or regulations.

15.5 Insurance and Compensation for Injury

Each subject in the study must be insured in accordance with the regulations applicable to the site where the subject is participating. If a local underwriter is required, then the sponsor or sponsor's designee will obtain clinical study insurance against the risk of injury to clinical study subjects. Refer to the Clinical Study Site Agreement regarding the sponsor's policy on subject compensation and treatment for injury. If the investigator has questions regarding this policy, he or she should contact the sponsor or sponsor's designee.

Appendix A Schedule of Study Procedures

Study Day/Week:	Screening Days -28 to -1	Treatment										Final safety Visit/ Early Termination Visit Week 100 (b)	Observational Follow-up visit (c)
		Wk 0/ Day 1/first dose (a)	Wk 12	Wk 24	Wk 36	Wk 48	Wk 60	Wk 72	Wk 84	Wk 96/ last dose			
Visit Windows (Days):	NA	NA	±5d	±5d	±5d								
Visit Number:	1	2	3	4	5	6	7	8	9	10	11		
Informed consent	X												
Inclusion/exclusion criteria	X												
Demographics and medical history	X												
Medication history	X												
Physical examination	X					X						X	X
Vital signs	X	X	X	X	X	X	X	X	X	X		X	X
Weight and height	X	X	X	X	X	X	X	X	X	X		X	X
Concomitant medications	X	X	X	X	X	X	X	X	X	X			
Concurrent medical conditions	X												
Predicted adult height (d)	X					X				X			X
Tanner staging evaluation	X	X	X	X	X	X	X	X	X	X		X	X
Bone age (e)	X			X		X		X		X			X
Hematology	X			X		X		X				X	X
Urine analysis	X				X							X	
Urine Pregnancy test (f)		X											
Pregnancy avoidance counseling	X	X	X	X	X	X	X	X	X	X		X	
Clinical chemistry	X			X		X		X				X	X
ECG	X		X		X		X			X			X
Pelvic/Testicular ultrasonography (g)	X			X		X		X		X		X	X
LH and FSH				X		X		X					
Estradiol or Testosterone		X(j)	X	X	X	X	X	X	X	X		X	X
Stimulation test (h)	X		X							X			
Cranial MRI (i)	X												
CEA, AFP, β -HCG	X												
Bone mineral density (j)		X (j)										X	
Serum bone metabolism biomarker (k)		X(j)										X	
Injection investigational drug (l)		X								X			
PTE assessment	X	X											
AE assessment		X	X	X	X	X	X	X	X	X		X	X

CONFIDENTIAL

NA=not applicable.

(a) The day of first investigational drug administration for Treatment period is Day 1. The day before first investigational drug administration for Treatment period is Day -1.

(b) Conduct Final Visit procedures for subjects discontinued early per Section 7.6. The end of study is defined as the date of the last visit (Week 100) of the last subject undergoing the study unless the study is stopped earlier by sponsor due to futility or for safety reasons. Subjects who discontinued from the study for any reason will complete the Early Termination Visit/Final Safety Visit , 4 weeks after the last dose of leuprorelin.

(c) During the observational follow- up period, it is recommended to monitor the subjects who remain on treatment at least every 6 months or at a schedule based on the investigator's judgments until drug discontinuation to collect the following: height and weight, secondary sexual characteristics, hematology, clinical chemistry, ultrasonography, LH and FSH, estradiol or testosterone and ECG. ECG will also be performed 4 weeks after the last administration of leuprorelin. All subjects will be followed up annually after the last dose of leuprorelin until stable puberty is reached. At each visit, the following will be performed: Tanner staging, height and weight, BMI, menstrual history, and pelvic ultrasonography for girls. Stable puberty is defined as 2 years after menarche for girls or Tanner staging V of secondary sexual characteristics development for boys.

(d) Predicted adult height will be evaluated using Bayley-Pinneau method.

(e) Bone age will be evaluated by investigators at each site using TW3 standards or Greulich-Pyle standards at Screening. All bone age x-ray will be sent for central reading before the end of the study

(f) The female subject who, at the discretion of the investigator, is deemed to be of child bearing potential must provide negative urine pregnancy test at Day -1 or Day 1 prior to drug administration.

(g) Pelvic ultrasonography will be performed for females to measure, uterus size and number/size of follicles. For males, ultrasonography will be performed to measure the testicular volume. These results if available already can be used as part of screening. If result is already available – whether at same site or hospital – within 28 days prior to first dose, the result can be used for screening, under the condition that the Site retains a copy of the data in file notes as source documents.

(h) Stimulation test: Blood samples will be collected at 0, 30, and 60, minutes after the injection of GnRH. It is acceptable to use both GnRH and GnRHa in stimulation test; however, it is preferable to use GnRH as priority. These results if available already can be used as part of screening. If stimulation test result is already available – whether at same site or hospital – within 28 days prior to first dose, the result can be used for screening, under the condition that the Site retains a copy of the data in file notes as source documents. (i) Cranial MRI can consist of only pituitary scan, including saddle region.

(j) Bone mineral density will be evaluated by dual energy x-ray bone densitometry at selected sites, which can done at any time prior to the first dose after the Screening. Estradiol or Testosterone and Serum bone metabolism biomark also can be done at any time prior to first dose as part of screening visit. (k) Serum bone metabolism biomarker included phosphorus, 25-hydroxy vitamin D, osteocalcin, crosslaps. These 4 tests can be performed as per what is available at the given Site. These tests can done at any time prior to the first dose after the Screening.

(l) Subcutaneous injection Leuprorelin every 4 weeks. For the dosing visits between Visits 2-3, between Visits 3-4, between Visits 4-5, between visits 5-6, between visits 6-7, between 7-8, between 8-9, between visits 9-10: these visit window is +/- 2 days; in addition, the between gap between dosing cannot be less than 3 weeks (21 days).

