5.2 Endpoints

5.2.1 Primary Endpoint

Subject incidence of treatment-emergent adverse events (TEAE).

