6.0 STUDY DESIGN AND DESCRIPTION

6.1 Study Design

[figure not shown]
This is a phase 4, open label study to be conducted in China, to assess long-term safety and efficacy of leuprorelin in the treatment of CPP. Approximately 300 subjects will be enrolled. The treatment duration is 96 weeks. The study will consist of 3 periods including a 4-week Screening Period, a 96-week Treatment Period and a 4-week Safety Follow-up Period. Followed by an observational follow-up period where subjects who remain on treatment will be observed at least every 24 weeks and after last dose all subjects will be followed up annually until stable puberty is reached.

Eligible CPP subjects with body weight ≥ 20 kg will receive the recommended dose of leuprorelin 3.75 mg SC every 4 weeks. Subjects with body weight <20 kg will receive recommended dose of 1.88 mg SC every 4 weeks. It is not recommended to exceed 180 μ g/kg. The dose can be adjusted based on subject's condition and investigator's judgment. Study visits, procedures, and evaluation are summarized in the Schedule of Study Procedures (Appendix A). Subjects will be followed until the end of the study, during which time they will be assessed by their treating physicians. serious adverse events (SAEs) and adverse events (AEs) will be recorded in the case report form (eCRF). Efficacy will be evaluated every 12 Weeks. The efficacy and safety data will be evaluated and submitted to CFDA.

Subjects will be given the first dose of study drug in the clinic at Day 1 (Visit 2, Week 0). The last dose of study drug will be given on the day of Week 96 (Visit 10). All dosing of study drug will take place in the clinic by appropriate site staff. End of study assessment will be conducted at Week 96 (Visit 10). All subjects who receive study drug will be required to have a Final Safety Visit (Visit 11) at approximately 4 weeks after the last dose.

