10.1.5 Severity of PTEs and AEs

The different categories of intensity (severity) are characterized as follows:

Mild: The event is transient and easily tolerated by the subject.
Moderate: The event causes the subject discomfort and interrupts the subject's usual activities.
Severe: The event causes considerable interference with the subject's usual activities.

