10.2.1.2 PTE and AE Reporting

At each study visit, the investigator will assess whether any subjective AEs have occurred. A neutral question, such as “How have you been feeling since your last visit?” may be asked. Subjects may report AEs occurring at any other time during the study. Subjects experiencing a serious PTE must be monitored until the symptoms subside and any clinically relevant changes in laboratory values have returned to baseline or there is a satisfactory explanation for the change. Non-serious PTEs, related or unrelated to the study procedure, need not to be followed-up for the purposes of the protocol.

All subjects experiencing AEs, whether considered associated with the use of the study medication or not, must be monitored until the symptoms subside and any clinically relevant changes in

CONFIDENTIAL

laboratory values have returned to baseline or until there is a satisfactory explanation for the changes observed. All PTEs and AEs will be documented in the PTE/AE page of the eCRF, whether or not the investigator concludes that the event is related to the drug treatment. The following information will be documented for each event:

1. Event term.
2. Start and stop date.
3. Severity.
4. Investigator's opinion of the causal relationship between the event and administration of study medication(s) (related or not related) (not completed for PTEs).
5. Investigator's opinion of the causal relationship to study procedure(s), including the details of the suspected procedure.
6. Action concerning study medication (not applicable for PTEs).
7. Outcome of event.
8. Seriousness.

Reporting of unexpected non-serious adverse drug reactions (ADRs):

For the non-serious AE which is not listed in the labeling, if it is potentially related to the study medication or study procedure, or if the causality is unknown/missed, the investigator should report this unexpected non-serious ADR to Takeda within 7 calendar days of first notification of the event. The AE page of the eCRF should be transmitted within 7 calendar days to the attention of the contact listed in Section 1.1. The investigator should make sure the success of the reporting transmission.

If the follow-up information of the unexpected non-serious ADR is received, the reporting of the follow-up information will follow the same reporting procedure of the initial report.

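### No adverse-event assessment is scheduled at 16 of the 25 injection visits, and the protocol does not say whether those dosing visits count as study visits

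*Protocol*

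**What the plan says.** The primary endpoint (Protocol 5.2.1) is the proportion of subjects with a treatment-emergent AE (TEAE). SAP 6.5.1 adds event counts per 100 patient-years and breaks both down by preferred term and system organ class.

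On dosing, Appendix A footnote (l) says "Subcutaneous injection Leuprorelin every 4 weeks", and Section 6.1 places the first dose at Week 0 and the last at Week 96. Section 6.1 also states: "All dosing of study drug will take place in the clinic by appropriate site staff".

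On assessment, Appendix A and Sections 9.3.2 to 9.3.11 list AE assessment at Visits 2 to 11 only, that is, at Weeks 0, 12, 24, 36, 48, 60, 72, 84, 96 and 100. Concomitant medication during treatment follows the same numbered visits. The injections between numbered visits are covered in footnote (l) ("For the dosing visits between Visits 2-3, between Visits 3-4, between Visits 4-5", continuing to Visits 9-10), which gives a window of ±2 days and a minimum gap of 21 days. No section lists an AE or concomitant-medication assessment for them. SAP Appendix A repeats the schedule and the footnote.

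On eliciting events, Section 10.2.1.2 says "At each study visit, the investigator will assess whether any subjective AEs have occurred". It offers a neutral, optional question that looks back to the last visit, and it lets subjects report events at any other time. Section 9.1.6 ties the concomitant-medication question to each study visit as well. Neither section says whether a dosing visit is a study visit.

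**The concern.** The study exists mainly to collect safety data (Section 4.2). It has a single open-label regimen and no concurrent control, so what is reported depends directly on how and when events are elicited. Site staff see each child every 4 weeks, yet the schedule asks about AEs at intervals of up to 12 weeks.

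The events most exposed to a long look-back are the mild ones, which Section 10.1.5 defines in these words: "The event is transient and easily tolerated by the subject". The first dose is a clear example. Section 4.1 describes a transient hormonal flare after it, with suppression usually within 2 to 4 weeks. The next scheduled AE assessment is at Week 12, although the child attends for injections at Weeks 4 and 8.

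The second issue is the undefined term. With approximately 10 to 15 sites, some may ask every 4 weeks and others every 12, all in compliance. SAP 6.1 summarises by males, females and all subjects, so no planned table would show such a difference. Any under-reporting would make the drug look safer, and events missed during conduct cannot be recovered at analysis.

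**Working it through.** The plan states no figure for this count, so there is nothing to reproduce. The inputs are the dosing interval and the first and last dose (Section 6.1, footnote l) and the AE row of Appendix A with Sections 9.3.2 to 9.3.11.

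**Coverage of injections**

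- Injections at Weeks 0, 4, ..., 96: 96/4 + 1 = 25.
- Injections on a visit with a scheduled AE assessment (Weeks 0, 12, ..., 96): 96/12 + 1 = 9.
- Injections without one: 25 − 9 = 16, and 16/25 = 64%. These are two in each of the 8 intervals between numbered visits: Weeks 4, 8, 16, 20, 28, 32, 40, 44, 52, 56, 64, 68, 76, 80, 88 and 92.

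**Lag from injection to the next scheduled AE assessment**

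| Injection weeks | Number | Lag now | Lag if every dosing visit has an assessment |
|---|---|---|---|
| 0, 12, ..., 84 (numbered visits) | 8 | 12 weeks | 4 weeks |
| 4, 16, ..., 88 | 8 | 8 weeks | 4 weeks |
| 8, 20, ..., 92, and 96 | 9 | 4 weeks | 4 weeks |

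Mean lag now: (8×12 + 8×8 + 9×4)/25 = 196/25 = 7.84 weeks. With the fix it is 4 weeks for every injection, and post-baseline assessments through Week 100 rise from 9 to 25.

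The longest lag follows injections given at numbered visits, not the 16 in between. The count of 16 describes the schedule and does not measure events lost.

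**What recall loss could do (illustration only)**

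Assume that each injection is followed by a given type of mild event with probability p, and that the event is reported with probability m^(lag/4), where m is the chance of retaining it over 4 weeks. Both p and m are assumptions, since the documents give no AE rate or recall figure.

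Events captured on the 12-weekly schedule relative to the 4-weekly one = (8m³ + 8m² + 9m)/(25m):

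- m = 0.5: 7.5/12.5 = 60%
- m = 0.7: 12.964/17.5 = 74%
- m = 0.9: 20.412/22.5 = 91%
- m = 1.0: 25/25 = 100%

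Subject incidence = 1 − product over injections of (1 − p × m^(lag/4)). At p = 0.02, 12-weekly against 4-weekly, it is 14.0% against 22.2% (m = 0.5), 23.0% against 29.7% (m = 0.7), 33.7% against 36.5% (m = 0.9), and 39.7% against 39.7% (m = 1.0).

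The proportionate loss in subject incidence shrinks as events become commoner, because one captured event per child is enough. At m = 0.7 and p = 0.05, the figures are 48.2% against 59.0%, a ratio of 0.82, compared with 0.74 for event counts.

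**The case against.** The strongest reply is that Section 10.2.1.2 already covers the dosing visits. Footnote (l) itself calls them visits, and Section 8.2 speaks of injecting at subsequent visits, so each study visit can naturally be read to include them. A reader might infer from Appendix A that 16 injections receive no AE assessment at all. The documents support only that none is scheduled there. The opposite reading is equally available, however. Section 6.1 says that study visits are set out in Appendix A, and Section 9.3 says that assessments belong to the designated visit. The ambiguity stands.

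The reply also notes that nothing falls outside collection. Section 10.2.1.1 makes it continuous from first dose to Visit 11, subjects may report at any time, and the next numbered visit looks back over the gap. That is correct, and it limits the concern to how well events are elicited.

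A reader might go further and conclude that AEs are under-counted, that sites do differ, or that the loss is greatest after the 16 in-between injections. The first two are plausible inferences without supporting data in the documents. The third is contradicted by the lags above. Nor is there a hypothesis test or safety threshold (Section 13.3) that a changed rate would be shown to cross.

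**Conclusion.** The point holds as a gap in the schedule joined to an undefined term. Sixteen of 25 injection visits have no scheduled AE assessment, and the mean lag from injection to the next scheduled assessment is 7.84 weeks, where 4 is attainable at visits the children already attend. These counts are exact and assume only that dosing follows the planned calendar.

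The consequence is a risk of under-ascertaining mild, transient events and of differences between sites. It bears mainly on term-level incidence and rates per 100 patient-years. The incidence of any TEAE is proportionately less exposed, since a single recalled event in 96 weeks suffices. The size cannot be derived from the documents. In the illustration, relative capture runs from 60% to 100%, and the effect vanishes if recall is complete or if sites already ask at every dosing visit. This does not invalidate the primary endpoint. It should be fixed because the improvement is cheap.

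**What to change.** State in Section 10.2.1.2 that study visit includes the 4-weekly dosing visits. Add to Appendix A footnote (l) and Section 9.3 that the existing neutral AE question and the concomitant-medication question are asked at every dosing visit and the answers recorded in the eCRF. Carry the footnote into SAP Appendix A. Every injection is then followed by a scheduled assessment about 4 weeks later.

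A directed question about injection-site reactions is not needed. It would solicit one event type by a different method from the neutral question.

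The cost is protocol and eCRF wording, plus a few minutes and some data entry at visits where site staff are already present and, under Section 9.2, already record the supplies used. The observed TEAE incidence may be higher as a result.
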